9.1.5 Non-Hematologic Adverse Events Related to PF-07901801 Administration

PF-07901801 (TTI-622) dose adjustments based on the occurrence of non-hematologic treatment-related adverse events are described in Table 17.

Table 17. Management of Non-Hematologic Adverse Events Associated with PF-07901801 Administration

Observation	Management Guidelines
Grade ≥3 events with the following exceptions: • Nausea and/or vomiting lasting <72 hours with supportive care	 For Grade 3 events, delay PF-07901801 dosing until the re-treatment criteria are met, then resume PF-07901801 at one dose level reduction No dose reduction is required for the exceptions listed
 Fatigue lasting ≤72 hours Laboratory abnormalities lasting <72 hours and judged by the investigator as not clinically significant 	• For Grade 4 events, discontinuation of PF-07901801 should be considered unless the adverse event was transient and/or asymptomatic and/or not clinically significant. If the investigator judges that continued treatment may be in the participant 's best interest, PF-07901801 treatment can be resumed when the adverse event resolves to a level that meets re-treatment criteria. In consultation with the medical monitor, the dose level may be reduced.

9.1.6 Management of Other Adverse Events Related to PF-07901801 Administration

PF-07901801 dose adjustments based on the occurrence of other treatment-related adverse events are described in Table 18.

Table 18. Management of other Treatment-Related Adverse Events

Severity of Event	Management Guidelines	
C 1 1	Maintain PF-07901801 dose level	
Grade 1	Provide treatment to control symptoms if applicable	
C 1- 2 (4-111-)	Maintain PF-07901801 dose level	
Grade 2 (tolerable)	Provide treatment to control symptoms if applicable	
Grade 2 (intolerable)	• Hold administration of PF-07901801 until the adverse event recovers to Grade ≤1 or to baseline level, then resume treatment with PF-07901801	
Grade 3	 Hold administration of PF-07901801 until the adverse event recovers to Grade ≤1 or to baseline level, then resume treatment with PF- 07901801 	
Grade 4	Discontinue PF-07901801 unless participant is receiving disease control, adverse event recovers to baseline level and treating physician recommends continuation of treatment at a lower dose level or under a modified schedule	

9.1.7 Grading and Management of Infusion-Related Reactions

Infusion-related reactions are not expected to be prevalent in this study. However, in the event that infusion-related reactions are observed, they will be graded as described in Table 19. Guidelines for management of infusion-related reactions are provided in Table 20.

Table 19. Definition of Infusion-Related Reaction by CTCAE Grade

CTCAE Grade	Definition
Grade 1 Infusion-Related Reaction	Mild transient reaction; infusion interruption not indicated; intervention not indicated
Grade 2 Infusion-Related Reaction	Therapy or infusion interruption indicated but responds promptly to symptomatic treatment (e.g., anti-histamines, NSAIDS, narcotics, IV fluids); prophylactic medications indicated for ≤ 24 hours
Grade 3 Infusion-Related Reaction	Prolonged (i.e., not rapidly responsive to symptomatic medication, brief interruption of infusion, or both); recurrence of symptoms following initial improvement; hospitalization indicated for clinical sequelae
Grade 4 Infusion-Related Reaction	Life-threatening consequences: urgent intervention indicated

Note: An acute infusion reaction may occur with an agent that causes cytokine release (e.g., monoclonal antibodies or other biological agents). Signs and symptoms usually develop during or shortly after drug infusion and generally resolve completely within 24 hours of completion of infusion. Signs/symptoms may include: allergic reaction/hypersensitivity (including drug fever); arthralgia (joint pain); bronchospasm; cough; dizziness; dyspnea (shortness of breath); fatigue (asthenia, lethargy, malaise); headache; hypertension; hypotension; myalgia (muscle pain); nausea; pruritis/itching; rash/desquamation; rigors/chills; sweating (diaphoresis); tachycardia; tumor pain (onset or exacerbation of tumor pain due to treatment); urticaria (hives, welts, wheals); vomiting.

Table 20. Management of Infusion-Related Reactions Associated with PF-07901801 Administration

CTCAE Grade	Management Guidelines
	• The infusion may be stopped or continued at a reduced (50%) infusion rate at the discretion of the investigator.
Grade 1 Infusion- Related Reaction	• If symptoms resolve, the infusion can be re-started or increased, as tolerated, to the baseline rate.
	• The participant may receive appropriate further treatment for infusion-related reaction if clinically indicated per the site's standard practice for management of IRR.
	The infusion should be stopped.
Grade 2 Infusion- Related Reaction	• The participant should receive appropriate further treatment with an anti-histamine and/or acetaminophen if clinically indicated per the site's standard practice for management of IRR. Further medications can be administered if necessary.
Totaled Teachon	• Once symptoms have resolved or reduced to Grade 1, the infusion can be continued at a reduced (50%) infusion rate. If after one hour the participant's symptoms do not return and vital signs are stable, the infusion rate may be increased every 30 minutes, as tolerated, to the baseline rate.
	The infusion should be stopped promptly.
	• The participant must receive appropriate treatment with an anti-histamine and/or acetaminophen and/or methylprednisolone or equivalent and, if necessary, further medications (i.e., epinephrine, bronchodilator).
Grade 3 Infusion- Related Reaction	• Only after the complete resolution to Grade ≤1, and after having received appropriate prophylactic medication(s) as described above, the infusion may be resumed at an infusion rate of 25%. If after one hour the participant's symptoms do not return and vital signs are stable, the infusion rate may be increased to a maximum of 50%.
	• If after the resumption of infusion, symptoms return (irrespective of grade), the infusion must be stopped and the infusion tubing should be disconnected.
	The duration of infusion may be prolonged in order to ameliorate IRR but PF-07901801 dose does not require reduction.
	• the sponsor medical monitor should be apprised of any ≥ G3 IRR that occurs during the study
	The infusion should be stopped promptly and the infusion tubing should be disconnected.
Grade 4 Infusion-Related Reaction	• The participant should receive appropriate treatment with an anti-histamine and/or acetaminophen and/or methylprednisolone (or equivalent) and, if necessary, further medications (i.e., epinephrine, bronchodilator).
	 After discussion with the sponsor medical monitor, the participant must not receive further infusions of PF-07901801 if PF-07901801 is judged by the investigator to be the cause of the infusion-related reaction and the investigator feels that implementation of alternative or more aggressive prophylaxis would not be sufficient.

9.2 Management of Adverse Events Associated with PLD

General guidelines for dose modifications in response to observed adverse events is presented in this section. In consideration that PLD is being used as a standard of care anti-cancer therapy in the enrolled participant population and based on investigator and site experience with PLD in the enrolled participant population, alternate dose modifications may be implemented after discussion with the medical monitor. In general, the PLD dose should not be increased after a dose reduction for toxicity; on a participant -specific basis, the investigator may discuss a dose increase with the sponsor medical monitor.

9.2.1 PLD Treatment Interruptions

Treatment with PLD may be temporarily suspended for up to 56 days to allow for resolution of adverse events. Dose interruptions for reason(s) other than toxicity and re-treatment may be allowed in accordance with standard of care if the participant is receiving disease control and after discussion with the sponsor medical monitor. In general, if an interruption of more than 56 days is required due to adverse events, PLD will be permanently discontinued; however, if in the judgment of the investigator, the participant is likely to derive disease control from PLD after a hold of more than 56 days, study drug may be re-started with approval of the sponsor medical monitor. Longer interruptions may be acceptable on a participant-by-participant basis at the discretion of the investigator after discussion with the sponsor medical monitor.

9.2.2 PLD Re-Treatment Guidelines

The laboratory parameters described in Table 21 should be met for re-treatment with PLD (i.e., initiation of a new cycle).

Table 21. Requirements for Re-Treatment with PLD

Parameter	Criterion
ANC	$\geq 1.5 \times 10^9 / L$
Platelet Count	\geq 75 × 10 ⁹ /L
Bilirubin	$\leq 1.5 \times \text{ULN}$ ($\leq 2 \times \text{ULN}$ if hyperbilirubinemia is due to Gilbert's
	syndrome)
AST, ALT	\leq 3 × ULN (<5 × ULN if liver metastases)
Treatment-Related Adverse Event	NCI CTCAE Grade <2 or baseline level (except for alopecia)

9.2.3 PLD Dose Modification Guidelines

Table 22 describes PLD dose reduction levels in the case of PLD-related adverse events.

Table 22. PLD Dose Modifications

Dose Level	First Dose Reduction	Second Dose Reduction
40 mg/m^2	30 mg/m^2	22.5 mg/m^2

If more than two dose reductions are required for a participant, the investigator should consult with the sponsor medical monitor to determine the appropriate course of action for the participant.

In case a participant's bilirubin level is elevated >1.2 mg/dL due to impaired liver function, the dose of PLD should be reduced as follows: serum bilirubin 1.2 to 3.0 mg/dL - give ½ normal dose; serum bilirubin > 3 mg/dL - give ¼ normal dose.

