6.2 Inclusion Criteria

Participant must meet all the following criteria to be enrolled in the study:

General

- 1. Written informed consent obtained prior to performing any study-specific procedure, including screening procedures
- 2. Females \geq 18 years of age
- 3. ECOG Performance Status 0 or 1

Disease Characteristics

4. Histologically-confirmed epithelial ovarian cancer (EOC), fallopian tube carcinoma (FTC) or primary peritoneal carcinomas (PPC).

Eligible histological subtypes are:

- Adenocarcinoma NOS
- Clear cell adenocarcinoma
- Endometrioid adenocarcinoma
- Malignant Brenner's tumor
- Mixed epithelial carcinoma
- Mucinous adenocarcinoma
- Serous adenocarcinoma
- Transitional cell carcinoma
- Undifferentiated carcinoma
- 5. Platinum-resistant recurrent disease, defined as disease progression ≤6 months after the most recent platinum-based treatment regimen (date calculated from the last administered dose of platinum) or the participant is no longer able to receive or declined treatment with platinum-based chemotherapy
 - Includes standard of care therapies, including platinum-based therapies, PARP inhibitors (Poly ADP Ribose Polymerase) or bevacizumab in the

platinum-sensitive setting or intolerability to such therapies or participant refusal

6. Measurable disease per RECIST v1.1; target lesions must not be chosen from a previously-irradiated field unless there has been radiographically and/or pathologically documented tumor progression in that lesion prior to enrollment.

Organ Function

Adequate organ and hematologic function as defined below:

- 7. Serum AST and ALT ≤ 3 x upper limit of normal (ULN); ≤ 5 x ULN in the presence of liver metastasis
- 8. Serum bilirubin (total) \leq 1.5 x ULN (\leq 2 x ULN if hyperbilirubinemia is due to Gilbert's syndrome)
- 9. Serum creatinine ≤1.5 x ULN OR creatinine clearance/estimated glomerular filtration rate (eGFR) ≥40 mL/min/1.73 m² if serum creatinine is >1.5 x ULN
- 10. Hemoglobin ≥9 g/dL; packed red blood cell transfusions are not allowed in the two weeks preceding screening evaluation
- 11. ANC > 1.5×10^9 /L
- 12. Platelet count $\geq 100 \times 10^9/L$
- 13. Left ventricular ejection fraction (LVEF) determined by echocardiogram or multigated acquisition scan >50% at screening

Previous Therapy

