12.2 Analysis Populations

The following analysis populations are defined for the study:

Safety Population: all participants who received at least one dose of PF-07901801

DLT-Evaluable Population: all participants in Phase 1 who either experience DLT after at least one dose of PF-07901801 or did not experience a DLT and received the full dose of PLD and at least two infusions of PF-07901801 and completed safety evaluations during the 28-day Cycle 1 DLT period.

PF-07901801 and PLD Concentration Analysis Population: all participants who received at least one dose of PF-07901801 or PLD and have at least one evaluable blood sample for analysis collected.

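### From Cycle 2, the bilirubin rule in Protocol 9.2.3 directs reduced PLD doses at values that do not meet the Table 21 re-treatment criterion, and nothing says which governs

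*Protocol*

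**What the plan says.** Protocol 9.2.2 introduces the re-treatment table as follows: "The laboratory parameters described in Table 21 should be met for re-treatment with PLD". It explains re-treatment as the start of a new cycle. The bilirubin row of Table 21 sets a limit of 1.5 x ULN, or 2 x ULN if the elevation is due to Gilbert's syndrome. No dose is attached.

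Protocol 9.2.3, the next section, works in absolute units. It applies above 1.2 mg/dL, and only where impaired liver function is the cause. Its first step reads "serum bilirubin 1.2 to 3.0 mg/dL - give ½ normal dose". For values beyond 3 mg/dL, PLD falls to a quarter of the usual amount. The section does not refer to Table 21, and Table 21 does not refer to it.

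Three other places matter:

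- Inclusion criterion 8 (Protocol 6.2) uses the same ULN multiples as Table 21 and states no dose.
- Protocol 5.2.1 gives PLD as 40 mg/m² on Day 1 of each 28-day cycle, with no cross-reference to 9.2.3.
- The DLT-evaluable population in Protocol 12.2 takes in a participant who "did not experience a DLT and received the full dose of PLD", together with at least two PF-07901801 infusions and completed Cycle 1 safety evaluations. SAP 5.6.2 says the same. The Protocol Synopsis, 5.1 and 5.2 (notes to Table 11) ask only that PLD was received on Day 1, with no condition on the amount.

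**The concern.** The two adjacent sections answer the same question, what to do with PLD at a given bilirubin value, on different scales and with different answers. Above the Table 21 limit one withholds the drug and the other gives a reduced dose. That bears on participant safety. It also means PLD exposure from Cycle 2 could depend on which section a site reads first.

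There is a secondary effect on the dose-escalation analysis. Nothing in 9.2.3 limits it to later cycles, so a Phase 1 participant who is eligible under criterion 8 but has hepatic bilirubin elevation above 1.2 mg/dL could receive half the PLD dose in Cycle 1. With three to six participants per dose level, whether she counts as evaluable can change the 3+3 denominator.

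**Working it through.** The plan states no figure to reproduce. The check compares thresholds.

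**Inputs.** From 9.2.3: half dose at 1.2 to 3.0 mg/dL, quarter dose above 3 mg/dL, both for impaired liver function. From Table 21: 1.5 x ULN (2 x ULN in Gilbert's). From 5.2.1: PLD on Day 1 of each cycle, so from Cycle 2 every PLD dose starts a new cycle and comes under Table 21. The bilirubin ULN is not in the documents. It is an assumption here, taken as 1.0 to 1.3 mg/dL with break-even values shown.

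**Formulae.**

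- Table 21 limit = 1.5 x ULN.
- Width of the half-dose range = 3.0 − 1.2 = 1.8 mg/dL.
- Share of that range failing Table 21 = (3.0 − 1.5 x ULN) / 1.8.

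| Assumed ULN (mg/dL) | Table 21 limit, 1.5 x ULN | Half dose directed, Table 21 not met | Share of half-dose range | Gilbert's limit, 2 x ULN |
|---|---|---|---|---|
| 1.0 | 1.50 | above 1.50, to 3.0 | 1.50/1.8 = 83% | 2.0 |
| 1.1 | 1.65 | above 1.65, to 3.0 | 1.35/1.8 = 75% | 2.2 |
| 1.2 | 1.80 | above 1.80, to 3.0 | 1.20/1.8 = 67% | 2.4 |
| 1.3 | 1.95 | above 1.95, to 3.0 | 1.05/1.8 = 58% | 2.6 |

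**Quarter-dose range.** Every value above 3 mg/dL exceeds the Table 21 limit at each of these ULNs, including the Gilbert's limit.

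**Break-even values.** The half-dose conflict disappears only when 1.5 x ULN reaches 3.0, that is, at ULN = 3.0/1.5 = 2.0 mg/dL or more. Outside Gilbert's, a quarter dose could be given within Table 21 only if the ULN exceeded 2.0 mg/dL.

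**Below the Table 21 limit.** The range from 1.2 mg/dL to 1.5 x ULN exists for any ULN above 1.2/1.5 = 0.8 mg/dL. Here criterion 8 and Table 21 permit treatment, and 9.2.3 sets a half dose of 40/2 = 20 mg/m². These can all be followed together.

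**DLT evaluability.** Take a DLT-free Phase 1 participant given 20 mg/m² on Cycle 1 Day 1, with at least two PF-07901801 infusions and completed safety evaluations. Under Protocol 12.2 and SAP 5.6.2 she is not evaluable, because the PLD dose was not full. Under the Synopsis and Protocol 5.1 and 5.2 she is evaluable, because PLD was given on Day 1. The replacement rule (Protocol 5.2, SAP 8.3) describes non-evaluability as not receiving PLD and at least two PF-07901801 doses, so it does not clearly cover her.

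**The case against.** Several points on the other side stand.

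- Table 21 is worded as a recommendation within guidelines. Protocol 9.2 allows alternate dose modifications after discussion with the medical monitor. This softens the conflict, but sets no default between the two rules.
- The sections can be read in sequence: Table 21 decides whether a cycle starts, then 9.2.3 decides how much PLD is given. On that reading the half-dose range would stop at 1.5 x ULN, not 3.0 mg/dL, and, at the ULNs assumed here, the quarter-dose line could never be used from Cycle 2. The text of 9.2.3 says neither.
- 9.2.3 covers only elevation due to impaired liver function, so the Gilbert's allowance need not conflict with it.

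A reader might also infer more than the documents support:

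- *That the rules conflict from 1.2 mg/dL upward, half against full dose.* Criterion 8 and Table 21 state no dose. A reduced dose inside a permitted range is a layered rule.
- *That the dose or no-dose conflict arises at Cycle 1 Day 1.* Table 21 governs re-treatment only, so it does not apply to the first dose, even if bilirubin rises after screening.
- *That 20 and 10 mg/m² are errors because Table 22 omits them.* Table 22 covers reductions for PLD-related adverse events. The bilirubin rule has a separate basis.
- *That the fixed PLD backbone is lost.* The protocol plans for PLD reductions, and the SAP (8.1 and 8.2.2) summarises dose reductions and relative intensity.

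On evaluability, leaving out a half-dose participant would fit an MTD defined with PLD at 40 mg/m². That supports one definition over the other, but does not explain why both are in the documents.

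**Conclusion.** Protocol 9.2.2 and 9.2.3 contradict each other as written, from Cycle 2, for bilirubin above 1.5 x ULN in a participant with impaired liver function. At an assumed ULN of 1.0 to 1.3 mg/dL this affects 58% to 83% of the half-dose range and all of the quarter-dose range. These are shares of the bilirubin scale, not of participants, and the documents do not allow the number affected to be estimated. The existence of the conflict does not depend on the exact ULN: it holds for any value below 2.0 mg/dL.

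The Cycle 1 point is smaller. There is no contradiction over dose there, but the documents disagree on whether a DLT-free participant with a bilirubin-reduced PLD dose is DLT-evaluable. No view is taken on which threshold or dose is right.

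**What to change.** Reconcile Protocol 9.2.3 with Table 21 so that each bilirubin range has one PLD instruction, on one scale or with an explicit statement of which section governs. The sponsor decides the rule. State whether the bilirubin rule applies to the Cycle 1 dose, and cross-refer to it from 5.2.1 if so.

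Align the DLT-evaluable definitions in the Protocol Synopsis, 5.1, 5.2 and 12.2 and in SAP 5.6.2 on whether a bilirubin-reduced Cycle 1 PLD dose counts, and make the replacement rule in Protocol 5.2 and SAP 8.3 match.

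The cost is a wording amendment to the protocol and a matching edit to the SAP. Sample size, assessments and analysis methods do not change.

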9.2.4 Management of Infusion-Related Reactions Associated with PLD

Infusion-related reactions will be graded as described in Table 19. Management of infusion-related reactions associated with PLD administration are described in Table 23.

Table 23. Management of Infusion-Related Reactions Associated with PLD

CTCAE Grade	Management Guidelines	
	Slow the infusion rate or stop the infusion	
Grade 1	 Provide appropriate further treatment for infusion-related reaction if clinically-indicated per the site's standard practice. 	
Grade 2 Grade 3	• If symptoms resolve, the infusion can be re-started at a reduced infusion rate.	
	 Consider premedications and reduced infusion rate for subsequent infusions. 	
	Stop the infusion	
Grade 4	 Aggressively manage symptoms per the site's standard practice for management of PLD-associated or any infusion-related reaction Do not retreat with PLD 	

9.2.5 Management of Cardiomyopathy Associated with PLD

Doxorubicin hydrochloride, the active component of PLD, can cause myocardial damage, including acute left ventricular failure. The risk of cardiomyopathy is generally proportional to the cumulative exposure. Include prior use of other anthracycles or anthracenediones in calculations of cumulative dose. The risk of cardiomyopathy may be increased at lower cumulative doses in participants with prior mediastinal irradiation.

Because of the risk of cardiomyopathies with Doxorubicin it is important to assess left ventricular cardiac function prior to initiation of treatment. Participants will undergo baseline Left Ventricular Ejection Fraction (LVEF) determination by ECHO or MUGA scan to be performed at screening visit only. This evaluation may be repeated at any time during the study if clinically indicated.

9.2.6 Management of Hematologic Adverse Events Associated with PLD

Participants must have adequate hematological function with no transfusion or colony stimulating factor or erythropoiesis-stimulating agent for at least 2 weeks prior to Cycle 1 Day 1.

Primary prophylactic use of colony stimulating factors or erythropoiesis-stimulating agents or blood product transfusions are not permitted during the first 28 days of Phase 1 Cycle 1 (DLT evaluation period), unless indicated due to medical emergency.

Therapeutic and prophylactic use of G-CSFs is allowed per ASCO and NCCN guidelines. Management of hematologic adverse events associated with PLD administration is described in Table 24.

Table 24. Management of Hematologic Adverse Events Associated with PLD

CTCAE Grade	Management Guidelines
Grade 1 Neutropenia Grade 1 Thrombocytopenia	Resume treatment with no dose reduction
Grade 2 Neutropenia Grade 2 Thrombocytopenia	Hold administration of PLD until the adverse event recovers to Grade ≤1 or to baseline level, then resume treatment with no dose reduction
Grade 3 Neutropenia Grade 3 Thrombocytopenia	Hold administration of PLD until the adverse event recovers to Grade ≤1 or to baseline level, then resume treatment with no dose reduction
Grade 4 Neutropenia Grade 4 Thrombocytopenia	Hold administration of PLD until the adverse event recovers to Grade ≤1 or to baseline level, then resume treatment with first dose reduction

Management should be guided by the more severe toxicity if neutropenia and thrombocytopenia are both observed.

9.2.7 Management of Hand-Foot Syndrome Associated with PLD

Management of hand-foot syndrome (HFS) associated with PLD administration is described in Table 25.

Table 25. Management of Hand-Foot Syndrome Associated with PLD

CTCAE Grade	Management Guidelines
Grade 1: Mild erythema, swelling, or desquamation not interfering with daily activities	If no previous Grade 3 or Grade 4 HFS: no dose adjustment If previous Grade 3 or Grade 4 HFS: delay dose up to two weeks, then decrease dose by 25%
Grade 2: Erythema, desquamation, or swelling interfering with but not precluding normal physical activities; small blisters or ulcerations less than 2 cm in diameter	 Delay dosing up to two weeks or until resolved to Grade 0 - 1 Discontinue if no resolution after two weeks If resolved to Grade 0 - 1 with two weeks and: no previous Grade 3 or Grade 4 HFS: continue treatment at previous dose previous Grade 3 or Grade 4 toxicity: decrease dose by 25%
Grade 3: Blistering, ulceration, or swelling interfering with walking or normal daily activities; cannot wear regular clothing	Delay dosing up to two weeks or until resolved to Grade 0 – 1, then decrease dose by 25% Discontinue if no resolution after two weeks
Grade 4: Diffuse or local process causing infectious complications, or a bed-ridden state or hospitalization	 Delay dosing up to two weeks or until resolved to Grade 0 – 1, then decrease dose by 25% Discontinue if no resolution after two weeks

